4.2 Known Potential Benefits

General toxicity studies, reproductive and developmental toxicity studies, mutagenicity studies, antigenicity studies, general pharmacology studies, and PK studies have been satisfactorily completed without notable observations of concern. Edaravone was first approved in Japan in 2001 for acute ischemic stroke. The approved dosing regimen has been 30 mg/30 min intravenous (IV) infusion twice daily up to 14 days.

Although studies of many drugs have been evaluated for efficacy, no effective therapy to cure ALS has currently been established. Riluzole modestly extends life or the time to mechanical ventilation for subjects with ALS. Current ALS treatment is largely symptomatic or is instituted in response to physical impairment, such as gastrostomy for dysphagia and use of a respirator for dyspnea.

RADICUT® (edaravone) injection was approved by the Japanese Pharmaceuticals and Medical Devices Agency on June 26, 2015 and the US FDA on May 5, 2017 for the treatment of ALS as an IV formulation containing 30 mg edaravone in 100 mL solution. The approved dosage is 60 mg/60-minute IV infusion with 2-week on/off dosing cycles as follows:

- Initial treatment cycle: daily dosing for 14 days followed by a 14-day drug-free period.
- Subsequent treatment cycles: daily dosing for 10 days out of 14-day periods, followed by 14-day drug-free periods.

The Sponsor recognized that long-term frequent intravenous (IV) infusion might be inconvenient for certain subjects and caregivers, therefore, the development of an oral formulation of edaravone (MT-1186) was instituted. Since subjects with ALS may develop swallowing difficulties, oral suspension formulation of appropriate consistency and viscosity was developed for clinical trial use and ultimately as a to-be-marketed product.

Two-week toxicology studies in rodents (rats) and non-rodents (dogs) using the edaravone oral suspension was conducted in compliance with Good Laboratory Practice (GLP). The results demonstrated no new safety findings up to 300 mg/kg/day compared to safety events observed from previously reported IV administered toxicology studies. A 39-week toxicology study in non-rodents (dogs), and a 26-week study in rodents (rats) have completed.

The Sponsor has selected an oral dose showing similar PK parameters compared to IV 60mg edaravone.

Study MT-1186-J01

Study MT-1186-J01 was a Phase 1 study that evaluated the PK, safety, and tolerability of oral edaravone in healthy adult males following single and multiple oral doses. In each cohort of the single ascending dose sub-study (Part 1), 6 subjects received edaravone (30 mg to 300 mg) and 2 subjects received placebo. Subjects in Cohorts 1 to 6 were Japanese and subjects in Cohort 7 were Caucasian. In the multiple ascending dose substudy (Part 2), each cohort had 6 subjects on edaravone (120 mg and 200 mg) and 3 subjects on placebo.

Following increasing oral doses, edaravone was well absorbed with time to maximum concentration (t_{max}) values of 0.29-0.75 hr. The maximum concentration (C_{max}) and area under the concentration-time curve (AUC) of edaravone increased to a more than proportional degree within the dose range of 30 mg to 300 mg. The C_{max} and AUC after the administration of 120 mg oral edaravone suspension exceeded those of the 60 mg/60-minute IV marketed infusion. Approximately 105 mg of oral edaravone appears to be sufficient to achieve similar C_{max} and AUC values compared to those after 60 mg/60-minute IV marketed infusion. There was no statistically significant difference in the PK profile of edaravone between healthy Japanese and Caucasian subjects.

A significant food effect was observed following the oral administration of MT-1186. In the fed condition, MT-1186 C_{max} was reduced by approximately 80% and AUC was reduced by approximately 60% compared to those in the fasted condition. This result indicates that oral MT-1186 suspension should not be administered with a meal.

When edaravone (120 mg and 200 mg) was administered orally once daily (30 minutes before breakfast) for 5 days, no accumulations in C_{max} and/or AUC were observed for edaravone.

Study MT-1186-J02

Part 1: Drug-Drug Interaction (DDI) Study

Based on the results from in vitro drug-drug interaction (DDI) studies conducted according to the FDA Guidelines, the Sponsor decided that a clinical study to evaluate cytochrome P450 3A4 (CYP3A4) induction, breast cancer resistant protein (BCRP) inhibition, and an organic anion transporter 3 (OAT3) inhibition was necessary and other in vivo DDI studies were deemed not necessary.

Therefore, a clinical drug/drug interaction study was conducted and the pharmacokinetic profiles after single doses of 50 mg sildenafil (CYP3A4 substrate), 10 mg rosuvastatin (BCRP substrate) and 40 mg furosemide (OAT3 substrate) were compared to the PK profiles after single doses of those drugs alone and in combination with 120 mg of oral edaravone suspension, respectively. The oral dosing of edaravone at a dose of 120 mg did not have an effect on the PK of each substrate.

Part 2: Preliminary Regimen-Finding Study

In study MT-1186-J01, significant reductions in C_{max} and AUC values were observed. Therefore, in study MT-1186-J02, the timing of administration of edaravone relative to meals (1 hour before or 4 hours after a high-fat meal) was preliminarily investigated in Japanese healthy subjects. Dosing of edaravone 1-hour prior to a high fat meal produced a slightly lower C_{max} with the t_{max} occurring before 1 hour (prior to the meal) and a slightly lower AUC compared to C_{max} and AUC in the fasted condition. However, these are likely due to variability in PK data rather than a food effect because the t_{max} occurred prior to the meal, where conditions in both cohorts were identical. Dosing of edaravone 4 hours after a high fat meal reduced C_{max} to 55.9% and area under the concentration-time curve until 24 hours (AUC_{0-24h}) to 76.3%, compared to that previously observed under fasting conditions.

Study MT-1186-J03

Based on PK data obtained from previous studies in healthy volunteers, an oral suspension dose of 105 mg of edaravone is estimated to show an equivalent mean AUC compared to that of the 60 mg/60-minute IV infusion regimen. Therefore, PK profiles of 105 mg of oral edaravone suspension were compared to those of the 60 mg/60-minute IV regimen as the approved dose in a planned confirmatory PK study in a cross-over study design in Japanese healthy subjects (n = 42).

This study demonstrated that the 105 mg oral suspension has an equivalent area under the concentration-time curve until infinity ($AUC_{0-\infty}$) to the approved 60 mg/60 min IV dose (geometric mean ratio [90% confidence interval (CI)]: 0.977 [0.917, 1.041]). The geometric mean ratio of C_{max} of the 105 mg oral suspension compared to 60 mg/60 min IV was also within bioequivalence range, but the upper limit of 90% CI exceeded 1.25 (geometric mean ratio [90% CI]: 1.217 [1.090, 1.359]).

The $AUC_{0-\infty}$ of the sulfate and glucuronide conjugates were 1.3 and 1.7 times higher after oral dosing of 105 mg MT-1186-J03 relative to that of the IV 60 mg/60-minute infusion, respectively.

Study MT-1186-J04

This was a clinical pharmacology study conducted to evaluate the PK of oral edaravone in subjects with ALS who were living independently (n = 9). The study compared the differences in the PK of subjects with ALS versus the PK in normal healthy subjects. No significant differences in the PK profile of edaravone were observed between healthy subjects and ALS subjects.

Study MT-1186-J05

This clinical pharmacology study was conducted to evaluate the PK of oral edaravone in ALS subjects when administered via a percutaneous endoscopic gastrostomy (PEG) tube. This study evaluated the difference in PK between edaravone suspension administered through a PEG tube versus historic oral administration in ALS subjects (Study J04) without a PEG tube. Preliminary data obtained from 6 completing ALS patients where oral edaravone suspension was administered via a PEG tube yielded exposures (AUC and C_{max}) that were slightly higher (~30%) than noted previously in Study J04. The range of exposures noted in Study J05 was within the range previously observed in normal Japanese subjects and ALS subjects without a PEG tube. This modest increase in exposure following administration of the suspension through a PEG tube is not considered clinically significant.

Study MT-1186-J06

The appropriate timings of oral administration relative to the timing and different types of meals were further investigated in this study. The results demonstrated that the following food conditions had little effects on the PK of MT-1186; an intake of high-fat meal (1000 calories, 50% fat) 8 hours before dose, or an intake of low-fat (normal) meal (400 calories, 25% fat) 4 hours before dose, or an intake of caloric supplement (e.g. ENSURE LIQUID) 2 hours before dose.

Study MT-1186-Z-101

This randomized, open-label, crossover, single dose clinical pharmacology study was conducted in 36 healthy volunteers to assess the comparative bioavailability of oral edaravone when administered via nasogastric tube (a surrogate for PEG/RIG administration) compared to oral administration. Preliminary PK data obtained from 36 subjects showed that both C_{max} and AUC fell within equivalence criteria. These data indicate that oral edaravone can be administered orally and via PEG/RIG without any need for dose adjustment.

Study MT-1186-A01

This study evaluated the safety of oral edaravone for a period of 48 weeks in patients with ALS. One hundred eighty five subjects were enrolled and 139 subjects in enrolled population were completed the 48-week study period. A total of 961 TEAEs were experienced by 175 (94.6%) subjects. Of these, TEAEs related to study treatment were reported by 46 (24.9%) subjects, serious TEAEs were reported by 48 (25.9%) subjects. The most frequently reported TEAEs by PT were fall (22.2%), muscular weakness (21.1%), and constipation (17.8%). The most frequently reported TEAEs related to study drug by PT were fatigue (3.2%), dizziness (2.7%), headache (2.2%), and constipation (2.2%). Twelve subjects died during the study period: 4 subjects died from respiratory failure, 2 subjects died from pneumonia, and 2 subjects died from ALS. The following causes of death were reported for 1 (0.5%) subject each: diabetic ketoacidosis and acute respiratory failure, feeding disorder, completed suicide, and lung disorder.

In order to evaluate the long-term safety of oral edaravone, Study MT-1186 A03 is ongoing as an extension study of Study MT-1186 A01. In addition, Study MT-1186-A02 and its extension study MT-1186-A04 are ongoing for the purpose of comparing the efficacy and safety of the following two dosing regimens of oral edaravone.

- Oral edaravone 105 mg administered once daily (regimen denoted as daily) in Cycles 1 through 12
- Oral edaravone 105 mg administered for 14 days, followed by placebo for 14 days in Cycle 1, and subsequently, repeat oral edaravone 105 mg administered for 10 days followed by placebo for 18 days (regimen denoted as on/off) in Cycles 2 through 12

Oral edaravone was approved by the US FDA (Radicava ORS ®) in 2022 as a new treatment option to delay disease progression in ALS patients.

5 STUDY OBJECTIVES, ENDPOINTS, AND HYPOTHESES

5.1 Study Objectives

5.1.1 Primary Objective

- To evaluate the long-term safety of oral edaravone at a dose of 105 mg administered once daily for 10 days out of a 14-day period, followed by a 14-day drug-free period. This study will be continued until the earlier date when oral edaravone is commercially available at each site in Japan or August 2023.

5.1.2 Exploratory Objective

- To evaluate the efficacy of oral edaravone at a dose of 105 mg administered once daily for 10 days out of a 14-day period, followed by a 14-day drug-free period. This study will be continued until the earlier date when oral edaravone is commercially available at each site in Japan or August 2023.

The subjects will be provided with the opportunity of taking oral edaravone by participating in this study.

5.2 Study Endpoints

5.2.1 Primary Safety Endpoints

The primary safety endpoints are to evaluate the safety of oral edaravone and include the following safety assessments.

- Adverse events (AEs), adverse drug reactions (ADRs)
- Physical examination, including neurological findings
- Body weight
- 12-lead electrocardiogram (ECG) parameters
- Vital signs (heart rate, respiratory rate, systolic and diastolic blood pressure, and axillary, oral or tympanic body temperature [the same measuring method had to be used throughout the study])
- Orthostatic vital signs
- Laboratory safety assessments (e.g., hematology, chemistry, urinalysis, and pregnancy)
- Columbia–Suicide Severity Rating Scale (C-SSRS)

5.2.2 Exploratory Endpoints

The exploratory endpoints are to evaluate the efficacy of oral edaravone and include the following assessments.

- Change in ALSFRS-R from baseline to each visit
- Presence or absence of event (death, tracheostomy or permanent assisted mechanical ventilation [\geq 23 hours/day]) (If yes, date of onset)

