Endpoints	
Primary Safety Endpoint: The safety of oral edaravone will be evaluated by the following safety assessments:
 
• AEs and adverse drug reactions• Physical examination;• Body weight;• 12-lead electrocardiogram (ECG) parameters;• Vital signs (heart rate, respiratory rate, sitting systolic and diastolic blood pressure, and axillary, oral or tympanic body temperature [method should be consistent throughout the study period]);• Orthostatic Vital Sign Measurement• Laboratory safety assessments (hematology, chemistry, urinalysis and pregnancy). 
Exploratory Efficacy Endpoints: The efficacy of oral edaravone will be evaluated by the following efficacy assessments:
 
• Score of ALS Functional Rating Scale-Revised (ALSFRS-R) at each visit• Events for death, tracheostomy or permanent assisted mechanical ventilation (≥ 23 hours/day) (If such events are found, the date of onset)

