Statistical Methods	
Continuous variables will be summarized descriptively using the number of observations (n), mean, SD, median, minimum, and maximum. Categorical variables will be summarized using frequency counts and percentages.
 
Determination of Sample Size: The study sample size is not based on power and statistical considerations but on the number of eligible subjects who will complete Week 96 of MT-1186-A03 or Week 48 of MT-1186-A04. Approximately 30 subjects plan to be enrolled in this study.
 
Analysis Set: Statistical analyses will be conducted based on the following analysis set.
 
Safety Analysis Set: The Safety Analyses Set (SAF) is defined as all subjects who received at least 1 dose of study drug in Study MT-1186-A301.
 
Study Medication Exposure: The duration of exposure in days will be calculated as follows: “Date of last dose of edaravone in MT-1186-A301” – “Date of first dose of edaravone in MT-1186-A301” + 1 If the date of first dose or the date of the last dose cannot be determined, then the duration calculation will not be completed. The duration of exposure will be summarized using descriptive statistics. All exposure data will be listed. Interruptions and compliance are not taken into account for calculations of duration of exposure.
 
Analysis for Exploratory Efficacy Endpoints: The ALSFRS-R scores will be listed descriptively at each visit. The number and percentage of events for death, tracheostomy or permanent assisted mechanical ventilation (≥ 23 hours/day) will be listed at each visit.
 
Analysis for Safety Endpoints: TEAEs will be summarized using the number of subjects and percentage by system organ class (SOC) and preferred term (PT) and will be presented as follows:
 
• TEAEs by SOC and PT• TEAEs by SOC, PT, and severity• TEAEs by SOC, PT, and drug relationship• TEAEs leading to discontinuation of study drug by SOC and PT
----------------------------	---

Name of Company	Mitsubishi Tanabe Pharma Corporation
Name of Investigational Product	Oral Edaravone
Name of Active Ingredient	Edaravone (3-methyl-1-phenyl-2-pyrazolin-5-one)

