	
• TEAEs leading to death by SOC and PT• TEADRs by SOC and PT• TEADRs by SOC, PT, and severity• Serious TEAEs by SOC and PT• Serious TEAEs related to study drug by SOC and PT 
Data collected from other safety evaluations will be summarized descriptively and/or listed according to the data type and will include the following:
 
• Body weight;• 12-lead ECG;• Vital signs (including orthostatic);• C-SSRS

Mitsubishi Tanabe Pharma Group

Protocol: MT-1186-A-301

Abbreviation: EOS = end-of-study, ET = early termination.

- a. Subjects will receive oral edaravone 105 mg once daily dosing for 10 days out of a 14-day period, followed by a 14 day drug free period. Oral edaravone will be administered following an overnight fast and subjects must continue to fast at least 1 to 2 hours post-dose before the next meal (e.g, breakfast).
- b. Evaluations for EOS will be performed at an earlier date of either “commercial oral edaravone available at each study site” or “August 31st,2023”. When commercial oral edaravone is available at each study site, the investigator should ask subjects to visit the study site and complete their EOS visit. If the EOS visit is completed prior to Week 24, no tests or evaluations for Week 24 will be done.
- c. When the treatment is discontinued prior to completion of the study, the investigator should complete the ET evaluations within seven days after the discontinuation.

Figure 1 : Study Schema

Table 1 : Schedule of Activities

Assessment	Week (window)	1 (x): Based on Week 96 of MT-1186-A03 or Week 48 of MT-1186-A04. No re-tests or evaluations will be performed for MT-1186-A-301 study	24 (± 7D)	EOS/ET ^a (± 7D)
Cycle	1	7		
Visit	1	2	3	
Informed consent	X			
Eligibility criteria	X			
Demographics ^b	X			
Vital signs ^c	(X)	X	X	
Orthostatic vital signs	(X)	X	X	
Pregnancy test (urine)	X	X	X	
Full Physical examination ^{d1}	(X)			X
Routine physical examination ^{d2}		X		
12-lead ECG ^e	(X)	X	X	
Body weight	(X)	X	X	
Event of death, tracheostomy or permanent assisted mechanical ventilation ^f	(X)	X	X	
Hematology ^g	(X)	X	X	
Chemistry ^h	(X)	X	X	
Urinalysis ⁱ	(X)	X	X	
Dispense edaravone ^j	X	X		
ALSFRS-R	(X)	X	X	
C-SSRS	(X)	X	X	
IMP compliance ^k	(X)	X	X	
Adverse events	(X)	X	X	

Abbreviation: D = Day; ECG = Electrocardiogram; C-SSRS = Columbia–Suicide Severity Rating Scale; ALSFRS-R = ALS functional rating scale- revised; EOS = End-of-study; ET = early termination.

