6 STUDY DESIGN

6.1 Overall Study Design

This is a Phase 3, multi-center, open-label safety extension study. The study will evaluate the long-term safety of oral edaravone at a dose of 105 mg administered once daily for 10 days out of 14, followed by a 14-day drug-free period. This study will be continued until the earlier date when oral edaravone is commercially available at each site in Japan or August 2023.

Eligible subjects who will complete Week 96 of MT-1186-A03 study or Week 48 of MT-1186-A04 study will be enrolled in this study (Study MT-1186-A-301). The subjects must continue to fast at least 1 to 2 hours post-dose before the next meal (eg, breakfast). The cycle of doses consists of 28 days, or a dose of 105 mg administered once daily for 10 days out of a 14-day period, followed by a 14-day drug-free period.

Subjects who discontinue from the study will complete the procedures listed in ET (refer to Table 1 for further information) within 7 days of discontinuation.

Further details can be found in the Study Schema (Figure 1).

This study will be continued as a post marketing study since the date of approval by the regulatory authority in Japan in order to provide the subjects with the opportunity of taking oral edaravone.

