15.3 Statistical Analyses

15.3.1 General Considerations

The statistical analysis will be performed using SAS® Version 9.4 or higher.

Continuous variables will be summarized descriptively using the number of observations (n), mean, standard deviation (SD), median, minimum, and maximum. Categorical variables will be summarized using frequency counts and percentages.

All individual subject data will be listed.

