1 INTRODUCTION

This statistical analysis plan (SAP) is based on the final protocol (01.00.00000) dated 9-JUN-2022. The plan covers statistical analysis, tabulations and listings of the study data to investigate the efficacy and safety.

Any statistical analysis details described in this document supersede any description of statistical analysis in the protocol.

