2.1.2 Exploratory Assessment(s)

- (1) ALSFRS-R score at each time of evaluation
- (2) Presence or absence of death, tracheostomy, or constant use of an assisted ventilator
(23 hours or more per day)
(If applicable, date of onset)

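### Protocol 5.2.2 makes ALSFRS-R change from baseline an exploratory endpoint, but the synopsis names the score, no ALSFRS-R baseline is defined, and no summary of change is planned

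*Protocol*

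**What the plan says.** The endpoint is stated in three places:

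- Protocol 5.2.2: "Change in ALSFRS-R from baseline to each visit".
- Protocol synopsis, Endpoints: "Score of ALS Functional Rating Scale-Revised (ALSFRS-R) at each visit".
- SAP 2.1.2: "ALSFRS-R score at each time of evaluation".

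The handling of the data is described in four places:

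- Protocol synopsis (Statistical Methods) and Protocol 15.3.3.2.1 carry the same sentence: "The ALSFRS-R scores will be listed descriptively at each visit".
- SAP 7.1.2.1 derives domain scores and gives a rule for missing items.
- SAP 8.1.5 summarises the total score by analysis visit and lists item, domain and total scores.

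On the reference point, Protocol Table 1 takes the Day 1 ALSFRS-R from the last parent-study visit and adds "No re-tests or evaluations will be performed for MT-1186-A-301 study". SAP 7.2 defines that visit (Week 96 of A03 or Week 48 of A04) as Day 1. It also reports that no subject reached Week 24 and that only EOS/ET will be used for analyses. SAP 9.2 still lists Day 1, Week 24 and EOS/ET as the visits to report.

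On precedence, SAP Section 1 states: "Any statistical analysis details described in this document supersede any description of statistical analysis in the protocol". SAP Section 10 records one departure from the protocol, the time point for the death, tracheostomy and ventilation events.

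**The concern.** A score at a visit and a change from baseline are different variables. The protocol names both for the same exploratory objective, and only the score is carried into an analysis. A reader of the report who starts from Protocol 5.2.2 will look for a change result, find none, and find no note explaining its absence.

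The choice affects what the study can say. In a single-arm study of a progressive disease, the exploratory efficacy objective is informative only through within-subject course. If SAP 7.2 is read literally and EOS/ET is the only visit tabulated, the ALSFRS-R output is one cross-section, which shows nothing about progression. If Day 1 is tabulated beside it, progression can be inferred only roughly from two separate summaries.

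The undefined baseline adds a smaller difficulty. Subjects roll over from A01 through A03 or from A02 through A04, so the word could in principle point to entry into the parent programme or to Day 1 here.

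**Working it through.** The documents give no ALSFRS-R standard deviation, correlation or expected change, so there is no plan figure to reproduce and no effect size to compute. The check is mainly textual.

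**1. Which variable is named, and which is analysed**

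| Place | Role | Variable |
|---|---|---|
| Protocol 5.2.2 | endpoint | change from baseline |
| Protocol synopsis, Endpoints | endpoint | score |
| SAP 2.1.2 | endpoint | score |
| Protocol synopsis, Statistical Methods | analysis | score |
| Protocol 15.3.3.2.1 | analysis (same sentence as the synopsis) | score |
| SAP 7.1.2.1 | derivation | domain scores |
| SAP 8.1.5 | summary and listing | total, item and domain scores |

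One of three endpoint statements names change. None of the four analysis places does; as two of them share one sentence, these are three distinct statements.

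**2. Whether baseline is defined anywhere**

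Apart from Protocol 5.2.2, the word appears in Protocol 4.1 (standard of care), Protocol 13.5 (return of abnormal laboratory results), and the demographics sections (Protocol 15.3.3.1 and SAP 8.1.4, which cover sex, age, ethnicity and race). None of these concerns ALSFRS-R. SAP 7.2 defines Day 1 without naming it baseline.

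**3. Whether the SAP removes the endpoint**

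The precedence sentence in SAP Section 1 covers descriptions of statistical analysis. Protocol 5.2.2 is an endpoint statement, and SAP Section 10, where departures are recorded, does not mention it.

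**4. Whether visit summaries could stand in for a change summary**

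Suppose both Day 1 and EOS/ET are tabulated, with standard deviations s1 and s2 and within-subject correlation r in the same subjects. Then

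Var(change) = s1² + s2² − 2·r·s1·s2.

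As r runs from −1 to 1, SD(change) runs from |s1 − s2| to s1 + s2. With s1 = s2 = s, the range is 0 to 2s and SD(change) = s·√(2(1 − r)). For illustration, with assumed correlations that are not from the documents:

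- r = 0.5: √1.0 = 1.00, so 1.00s
- r = 0.8: √0.4 = 0.632, so 0.63s
- r = 0.9: √0.2 = 0.447, so 0.45s
- r = 0.95: √0.1 = 0.316, so 0.32s

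Two visit tables therefore do not fix the spread of change, nor its median or range. For the mean, SAP 7.3 uses observed data without imputation. If some subjects have Day 1 but no EOS/ET score, then

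(EOS/ET mean) − (Day 1 mean, all) = (mean change, paired) + (Day 1 mean, paired) − (Day 1 mean, all).

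The last two terms cancel when the same subjects contribute to both visits, and otherwise only by chance.

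**5. Size of the gap**

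With no subject at Week 24, the missing quantity is one Day 1 to EOS/ET difference per subject, so about 30 values at the planned enrolment.

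**The case against.** The strongest reply is that the matter is editorial. The SAP is consistent about the variable, using the score from SAP 2.1.2 through 8.1.5, and its analysis text takes precedence. On that view one line in Protocol 5.2.2 is out of step and one line is missing from SAP Section 10. Four further points support this:

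- Day 1 is the only ALSFRS-R value before first dose in this study's schedule, SAP 7.2 ties it to this study, and neither document brings in scores from entry into A01 or A02. A parent-programme baseline therefore has little support.
- Missing scores should be few. Completing the parent visit is an entry condition, and subjects who discontinue "will complete the procedures listed in ET (refer to Table 1 for further information) within 7 days of discontinuation". SAP 6.1 reports both N and n, so unequal contribution would be visible.
- Protocol 15.3.1 says "All individual subject data will be listed", so change can be worked out by hand if Day 1 scores are in the listing.
- The variance range applies to any paired measurement and says nothing particular about this trial.

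Most of this stands and sets the severity. Day 1 is the natural baseline, the analysis variable under the SAP is clear, and the algebra shows only that visit tables cannot replace a change table. It is also fair that SAP 7.2 may be choosing between the two rows of its window table, Week 24 and EOS/ET, and leaving Day 1 in place. The objection does not remove the endpoint from Protocol 5.2.2, supply a definition of baseline, or provide the missing entry in SAP Section 10.

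**Conclusion.** The concern holds and is minor. The protocol states two different ALSFRS-R endpoints, one of them has no planned summary, its baseline is not defined, and the omission is not recorded. The loss is one descriptive table of at most one change value per subject. No primary or safety conclusion is affected, and no numerical bias can be stated because the documents give no ALSFRS-R variability.

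The practical importance depends on two points that the text leaves open. One is whether Day 1 will be tabulated: SAP 7.2 and 9.2 can be read either way, and without Day 1 the output cannot show progression at all. The other is whether Day 1 scores are in this study's database. The schedule marks them with a bracketed X. SAP Section 10 shows that such a mark did not guarantee collection for the event data, but that says nothing directly about ALSFRS-R.

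**What to change.** 1. In SAP 7.1.2.1, name Day 1 (Week 96 of A03 or Week 48 of A04) as the ALSFRS-R baseline and derive change in total score from Day 1 to EOS/ET.
2. In SAP 8.1.5, summarise that change in subjects with both values, using the statistics already set in SAP 6.1: n, mean, SD, median, minimum and maximum.
3. Make SAP 7.2 and 9.2 agree on the visits reported: Day 1 and EOS/ET, without Week 24.
4. Bring Protocol 5.2.2 and the synopsis to one endpoint statement.

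If the sponsor deliberately chose not to analyse change, an entry in SAP Section 10 saying so and giving the reason would close the point without steps 1 and 2. If the data are already fixed, Protocol Section 15 provides for describing deviations from the planned analysis in the study report.

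The cost is one derived variable, one table and a few lines of text, with no new visits or subjects. This assumes that the Day 1 scores are held in this study's database; if they are not, they must be transferred from A03 and A04.
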